7.1 Data Collection

An electronic case report form (eCRF) will be used in this study for all subjects who sign an ICF. Study site staff will use their own source data collection forms (except where noted as to be provided) or methods to capture required study information. Pertinent source data will be transcribed to eCRFs by study staff and the CRFs will be signed by the site investigator. The eCRF entry guidelines will be provided.

7.2 Data Validation

The data will undergo validation as described in the edit-check plan (or data validation plan) and data management plan. The study site will conduct a 100% quality control check of the source data. Furthermore, a quality control check of the source data against the eCRF will be followed as described in the data management plan. After or during entry into the database, edit checks will be performed as a validation method to check for errors and discrepancies such as missing data, data inconsistencies, and inappropriate data ranges. Data queries will be sent to the applicable site for resolution. Once all queries are resolved and applicable updates are made, edit checks will be rerun until all data are deemed clean.

7.3 Data Coding

The most current version of the Medical Dictionary for Regulatory Activities at the time of the first screening for the study will be used to code AEs and concomitant medications, and this version will be used for the entire study. Coding will be completed by a qualified member of the Cato Research.

7.4 Database Lock

Once all queries have been resolved, the clinical database has been deemed to be complete and clean, and appropriate prelock review of tables, figures, and listings has been done, the data manager will initiate the database lock approval and signature process. The sponsor will be required to provide database-lock approval.

Any changes to the data after database lock will be documented and approved by the sponsor before the database is updated.

7.5 Data Transfer

Upon completion of the study, the data will be transferred to the sponsor in SAS format with supporting SAS documentation, including the SAS programming codes according to the specifications of the sponsor. Subject names, date of birth (except year), and other personal identifiers will be removed from this data transfer file; any such information removed will be documented at the time of transfer.

8.0 Adverse Event Guidelines

8.1 Adverse Events

The following is the definition of an **AE**:

Any unfavorable and unintended sign (including an abnormal laboratory finding^a), symptom, or disease^b temporally associated with the use of a study product, **whether or not** related to the study product.^{12,13}

^a For this study, a laboratory AE is defined as an abnormal laboratory finding that is determined by the investigator to be clinically significant for that subject.

^b This includes a newly developed, worsened preexisting, recurring intermittent or intercurrent illness, injury, or condition.

All AEs occurring during this clinical trial after the subject has signed the ICF must be recorded in the CRF, including the date and time of onset and outcome of each event. Any condition existing prior to the use of a study product will be documented as a concomitant disease or condition and should be reviewed to determine whether or not the subject meets the inclusion and exclusion criteria.

Surgical procedures themselves are not AEs; they are therapeutic measures for conditions that require surgery. The condition for which the surgery is required may be an AE.

No causal relationship with the study products or with the clinical study itself is implied by the use of the term “adverse event.”

The investigator will review each event and rate each reported sign or symptom on a 3-point severity scale. The following definitions for **rating severity**¹³ will be used:

Mild: The AE is easily tolerated and does not interfere with daily activity.

Moderate: The AE interferes with daily activity, but the subject is still able to function.

Severe: The AE is incapacitating and requires medical intervention. Note: This is not the same as “serious,” which is based on the outcome or action criteria usually associated with events that pose a threat to life or functioning.

Each AE will also be assessed by the investigator for **relationship to study product (causality)** using the following grades of certainty^{14,15} (the strength of a causal association may be revised as more information becomes available):

Not related: Clearly and definitely due to extraneous cause (eg, disease, environment).

Unlikely:

- a. Does not follow a probable temporal (ie, time) sequence from use of study product.
- b. Does not follow a known pattern of response to the study product.
- c. Could plausibly have been produced by the subject’s clinical state/underlying disease or other drugs or chemicals the subject received.
- d. Does not reappear or worsen when the study product is re-administered.

Possible:

- a. Follows a reasonable temporal (ie, time) sequence from use of study product.
- b. Follows a known pattern of response to the study product.
- c. Could also have been produced by the subject’s clinical state/concurrent disease or other drugs or chemicals the subject received.

Likely:

- a. Follows a reasonable temporal (ie, time) sequence from use of study product.

- b. Follows a known pattern of response to the study product.
- c. Could not readily have been produced by the subject's clinical state/concurrent disease or other drugs or chemicals.
- d. Follows a clinically reasonable response on withdrawal (dechallenge) (ie, disappears or decreases when the study product is stopped or reduced).
- e. Rechallenge information is **not** required to fulfill this definition.

- Definitely:
- a. Follows a reasonable temporal (ie, time) sequence from use of study product.
 - b. Follows a known pattern of response to the study product.
 - c. Cannot be explained by the subject's clinical state/concurrent disease or other drugs or chemicals.
 - d. Follows a clinically reasonable response on withdrawal (dechallenge) (ie, disappears or decreases when the study product is stopped or reduced).
 - e. Recurs with re-exposure to study product (rechallenge). Note: Re-exposure of the subject is NOT required, but the "certainly/definitely related" category may only be used when recurrence is observed.

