1.2 Product Information

1.2.1 Preclinical Testing and Toxicological Assessment

Altria Client Services LLC implements an EVP toxicological assessment (“Product Stewardship”) program based on the concept that, while the use of any tobacco product has an inherent risk, ingredients and components used in Nu Mark’s products and any interaction of e-vapor device and e-liquid to form aerosols should not increase the inherent risk. The toxicological assessment is based on the totality of all of the available scientific evidence and, when appropriate, considers the harm reduction potential of EVPs for cigarette smokers.

Nu Mark uses the highest quality ingredients available, food-grade generally recognized as safe flavors and United States Pharmacopeia-grade aerosol formers (propylene glycol and glycerol) and nicotine. The use levels are determined based on estimated consumer usages, material-specific scientific data in the literature, and applicable regulatory information.

Toxicological data are already available for many individual ingredients commonly used in consumer products. However, there is no toxicological data on specific product formulations. Therefore, ALCS uses a weight-of-evidence approach in assessing e-vapor ingredients and products considering the following information:

- Individual material evaluation and risk assessment

- Chemistry analyses of formulations and product aerosols
- Flavor mixtures (prototype formulations): in vivo inhalation study in rats
- Product-specific formulation: in vitro (genotoxicity and cytotoxicity) testing

The approach is consistent with the FDA's recommendations in the Draft ENDS PMTA Guidance (May 2016), for "a full assessment of the toxicological profile associated with the new product, which includes in vitro and in vivo toxicological studies." In the assessment of genotoxicity potential, the FDA refers to International Council for Harmonization (ICH) S2(R1) guidance and Organization for Economic Cooperation and Development (OECD) protocols.^{7,8,9}

Altria Client Services LLC has performed the following battery of in vitro tests and if needed, in vivo genotoxicity test for the relevant e-liquid formulations can be performed:

1. In vitro bacterial gene mutation test (Ames assay; OECD471);
2. In vitro mammalian cytotoxicity test (Neutral Red Uptake [NRU] assay; OECD129);
3. In vitro mammalian genotoxicity test (micronucleus [MN] assay; OECD487); and

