1.2.3 Consumer Response Center Data

Adverse events (AE) related to the use of Nu Mark's e-vapor products (MarkTen®) have been spontaneously reported by consumers to the ALCS Call Center, "Consumer Response Center", since August 2013. While ALCS continuously monitors and evaluates these AEs, no investigation is conducted to verify these health-related complaints associated with the use of MarkTen® e-vapor products (approximately 59.6 million cartridges sold). As of December 31, 2016, there were 645 consumers who reported 1,206 AEs using the MedDRA Preferred Terms (PT). The top ten PTs were: thermal burns (11.19%), burns second degree (9.12%), throat irritation (5.22%), cough (5.06%), oral discomfort (4.89%), nausea (4.31%), headache (4.06%), burns first degree (3.98%), electric shock (2.74%), and dizziness (2.24%). There were four consumers who reported AEs that met the Common Terminology Criteria for Adverse Events v4.0 criteria for "Severe". The "Severe" PTs were: eye swelling, swelling face, swollen tongue, facial paralysis, cough, haematemesis, upper respiratory tract infection, gastrointestinal injury, aphonia, and thermal burn, with two consumers being hospitalized. The majority (79.44%) of the AEs reported to the Consumer Response Center were classified as "Mild".

Based on the information presented, it is anticipated that the four EVPs in this study will be well tolerated.

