7.4 ADVERSE EVENTS

All AE data for the safety population will be coded (to the lowest-level term) by using the Medical Dictionary for Regulatory Activities (MedDRA, Version 17.1). AEs will be listed in by-subject data listings, including verbatim term (investigator terms from the case report form), preferred term, test product, severity, and relationship to test product. Summary tables of frequency counts of AEs will be provided by primary system organ class (SOC), preferred term, and test product. Frequency counts of AEs will also be summarized by severity and relationship to test product and overall.

A PEAE is defined as an adverse event that:

- Emerges during exposure to a test product, having been absent previously, or:
- Worsens in severity during sessions within visits 2, when the adverse event is continuous in duration.

The incidence (%) will be determined by calculating the number of subjects with at least 1 event and the percentage of subjects with PEAEs by preferred term. The

Statistical Analysis Plan

incidence of PEAEs will be reported as the number (percentage) of subjects with PEAEs by SOC and preferred term. A subject will be counted only once within a SOC and preferred term, even if the subject experiences more than one PEAE within a specific SOC and preferred term. A missing or unknown value for the assessment will be considered worst. The number (percentage) of subjects with PEAEs will also be summarized by maximum severity (mild, moderate, or severe). If a given subject had more than one PEAE mapped to the same PT, then that PEAE will be represented according to the corresponding maximal level of severity.

The number (percentage) of subjects with PEAEs will also be summarized by relationship to test product. If a given subject had more than one PEAE mapped to the same PT, then that PEAE will be represented according to the strongest relationship to study product. Test product-related PEAEs include those adverse events considered by the investigator to be “definitely”, “possibly”, “probably”, “unlikely”, or “not” related to test product usage. The number (percentage) of subjects with test product-related PEAEs will also be summarized by maximum severity (mild, moderate, or severe).

The number (percentage) of subjects with serious adverse events (SAEs) will be summarized by MedDRA, SOC, and preferred term for each test product group. A subject data listing of all SAEs will be provided.

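### Every related causality grade in Protocol 8.1 requires a known pattern of response, so on the implied cumulative reading a new type of reaction with strong causal evidence fits none of the five grades

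*Protocol*

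**What the plan says.** Protocol 8.1 has the investigator assign one of five grades of certainty for relationship to study product, each defined by a short list or phrase. Possible, Likely and Definitely share item b: "Follows a known pattern of response to the study product". The reverse, "Does not follow a known pattern of response to the study product", appears only under Unlikely. Unlikely also lists "Does not follow a probable temporal (ie, time) sequence from use of study product" (item a), a plausible other cause (item c) and "Does not reappear or worsen when the study product is re-administered" (item d). Not related is kept for events that clearly have an extraneous cause.

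Two notes bear on how the lists are meant to work. Likely (e) exempts rechallenge information from what that definition requires. Definitely (e) does the opposite: "category may only be used when recurrence is observed".

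The grade is then used in three places. Protocol 8.2 asks for a causal assessment in the initial SAE report. Protocol 9.6 summarises event counts by relationship. SAP 7.4 states: "The number (percentage) of subjects with PEAEs will also be summarized by relationship to test product". SAP 7.4 also names its categories differently (*probably* where the protocol has *Likely*), and its description of test product-related events takes in every category, including *unlikely* and *not*.

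**The concern.** A causality scale should be able to record an unexpected effect when the evidence for it is good. Here the related grades all depend on the reaction already being recognised. Timing, dechallenge, rechallenge and absence of another cause cannot make up for novelty.

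The case is not far-fetched in this design. Each subject tries all four products at the Day -1 check-in. The subject then uses each one again on its assigned day, in two 10-puff collections and 12 hours of ad libitum use, with overnight abstinence between days. Exposure, withdrawal and re-exposure are built in, so the study can produce the evidence that the scale cannot use for an unfamiliar reaction.

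What is at stake is whether the relationship tables and the SAE causality field put such an event in the right place.

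**Working it through.** The plan gives no figure to reproduce. The check is logical and uses only the five definitions in Protocol 8.1.

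**Step 1: are the items cumulative?** The section does not say so. Exempting only rechallenge in Likely (e) makes sense if the other items are needed, and Definitely (e) makes recurrence mandatory. If any single item were enough, plausible timing alone would satisfy Possible, Likely and Definitely together, and the scale would not separate them. The cumulative reading is therefore the one implied.

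**Step 2: test one event against each grade.** Take an event with plausible timing, no known pattern and no other explanation, which stops on withdrawal and recurs on re-use.

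| Grade | Items met | Items failed |
|---|---|---|
| Definitely | a, c, d, e | b |
| Likely | a, c, d (e is a note) | b |
| Possible | a | b, c |
| Unlikely | b | a, c, d |
| Not related | none | no clear extraneous cause |

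No grade fits. If another cause could also have produced the event, Possible still fails on b and Unlikely still fails on a and d, so again none fits.

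**Step 3: is item b the obstacle?** Consider every profile without a known pattern: timing (2 levels) × other cause (4) × dechallenge (2) × rechallenge (recurs, does not recur, not done: 3) = 48.

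- With item b required, 0 of 48 reach Possible, Likely or Definitely.
- With item b ignored, 12 of 48 do. With plausible timing and another possible cause, 1 × 1 × 2 × 3 = 6 are Possible. With plausible timing, no ready other cause (2 levels) and positive dechallenge, 1 × 2 × 1 × 3 = 6 are at least Likely. The sum is 6 + 6 = 12.
- The event in Step 2 meets Likely and Definitely once item b is ignored.

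These counts show only that item b is what blocks the related grades. The profiles are not equally likely, so the counts say nothing about how often the problem would arise.

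**Step 4: which outputs depend on the grade?**

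| Depends on the grade | Does not depend on it |
|---|---|
| Causality in the SAE report (Protocol 8.2) | Recording of all events (Protocol 8.1) |
| Counts by relationship (Protocol 9.6, SAP 7.4) | Tables by organ class, preferred term and product (Protocol 9.6, SAP 7.4) |
| Product-related events by severity (SAP 7.4) | By-subject listings (beyond the relationship column); SAE reporting whether or not related (Protocol 8.2) |

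**Step 5: size.** One subject in 32 is 1/32 = 3.1% of a by-product table. The documents give no basis for predicting how many events would be affected.

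**The case against.** The strongest reply is that 8.1 describes a judgement scale. It speaks of grades of certainty, lets the grade be revised as information accrues, and nowhere says that all items must be met. An investigator could choose the best overall fit and grade the Step 2 event as Likely. *Known pattern* is also undefined and might be read broadly, for example to cover recognised nicotine effects. This stands in part: the gap depends on an implied reading. But best fit is not stated either, and a broad reading of item b does not reach a reaction that is new in kind. Investigators would have to supply a rule that the text lacks.

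Several stronger conclusions are tempting, and the documents do not support them.

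- *The event is sent to Unlikely.* It fails three of that grade's four items, and no text directs ungradable events there.
- *A safety signal would be lost.* Step 4 shows that it would still be recorded, listed and tabulated.
- *There is no product-specific toxicology, so any effect would be unexpected.* The sentence "However, there is no toxicological data on specific product formulations" in Protocol 1.2.1 invites this, but the same section goes on to report in vitro results for all four formulations.
- *Device injuries show how large the gap is.* The consumer reports in Protocol 1.2.3 are led by "thermal burns (11.19%), burns second degree (9.12%), throat irritation (5.22"%). Frequently reported injuries are a known pattern, so they pass item b. A burn that subsides can be graded Likely; only Definitely is withheld unless it recurs. Those reports do not measure this problem.

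SAP 7.4 also scores a missing or unknown assessment as worst. If that covers relationship, which is unclear, a blank grade would count as strongly related. Together with the SAP's all-inclusive description of related events, this masks the gap without closing it. An event graded Unlikely or Not related would still sit outside Possible, Likely and Definitely in the table by relationship.

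**Conclusion.** The point holds in a limited form. If the items in Protocol 8.1 are cumulative, as its rechallenge notes imply, a previously unreported type of reaction fits no grade even with good timing, no other explanation, positive dechallenge and recurrence. The investigator must then break the written definitions or leave the field empty, and the SAE causality field and relationship tables can misplace an unexpected product effect.

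The consequence is confined to those outputs. They are descriptive, no formal safety test is planned, and the number of affected events is probably small. The conclusion rests on the implied cumulative reading and on taking *known pattern* to mean a response already recognised for the product. It is an inexpensive improvement to the wording and does not show that safety surveillance in the study fails.

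**What to change.** In Protocol 8.1, keep item b of Possible, Likely and Definitely and add to each: *or is plausibly attributable to the product even if not previously reported*. Carry the same wording into the eCRF entry guidelines.

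At the same time, amend SAP 7.4 so that its relationship categories match the protocol scale (*Likely* instead of *probably*) and *unlikely* and *not* no longer count as test product-related.

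The cost is a few words in three documents, with IRB approval of the protocol revision under Protocol 10.1. No extra data, visits or staff are needed. The downside is that a few more events may be graded as related.

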8.2 Serious Adverse Events

The following is the definition for an **SAE**.

An SAE is any adverse study experience that results in any of the following outcomes:

- death
- a life-threatening adverse study experience^a
- in-patient hospitalization or prolongation of existing hospitalization
- a persistent or significant disability/incapacity^b
- a congenital anomaly/birth defect. ¹³

^a “Life-threatening” means that the subject was at immediate risk of death at the time of the SAE; it does not refer to an SAE that hypothetically might have caused death if it were more severe.

^b “Persistent or significant disability/incapacity” means that there is a substantial disruption of a person’s ability to carry out normal life functions.

An important medical event that may or may not result in death, be life-threatening, or require hospitalization may be considered an SAE when, based on appropriate medical judgment, it may jeopardize the subject and may require medical or surgical intervention to prevent one of the outcomes listed in this definition. An example is allergic bronchospasm requiring intensive treatment in an emergency room or at home.

All SAEs, **whether or not** considered study related, must be reported by telephone and by fax to the sponsor and Medical Monitor within 24 hours of the site's learning of the SAE or, at the latest, on the following workday. The contact information is as follows.

Sponsor Medical Contact:

[name].
Altria Client Services LLC
[contact]; Cellular: [contact]
[contact]

Medical Monitor:

[name]., Ph.D., RAC, DABT, PMP, CPI
[name]
[name]
[contact]
[contact]

The initial SAE report must be as complete as possible, including an assessment of the causal relationship between the event and the study product. Information not available at the time of the initial report (e.g., end date, laboratory values) must be documented on a follow-up SAE report. The SAE report forms and specific procedures for reporting SAEs will be provided separately.

In compliance with Good Clinical Practice (GCP) reporting guidelines, **the investigator must also inform the IRB and the site monitor of an SAE, whether or not** it is considered study related.

8.3 Adverse Event and Serious Adverse Event Follow-up

Each AE, including clinically significant laboratory abnormalities, whether serious or non-serious, will be followed until resolved, determined that follow-up is no longer required at the discretion of the investigator, or lost to follow-up, regardless of whether or not the subject is still participating in the study. Final outcome may be classified as resolved, improved, unchanged, worse, fatal, or unknown (lost to follow-up). When appropriate, medical tests and examinations will be performed to document the outcome of the AE.

